9.1 Study design

A retrospective cohort study design will be used to evaluate uterine perforation and IUD expulsion among women with an IUD insertion identified within EHR data. The study will consider the impact of breastfeeding status at the time of IUD insertion and timing of IUD insertion during the postpartum period on the outcomes of perforation and expulsion.

This study will include all women with evidence of an IUD insertion that had at least 12 months of enrollment history preceding IUD insertion. (RI, which does not have enrollment dates, will require a clinical visit at least 12 months before IUD insertion.) The 12-month enrollment before inclusion of IUD insertions will be used to gather baseline data, including data on the exposures, time postpartum, and breastfeeding.

Baseline data—such as patient demographics, patient characteristics (e.g., personal history of gynecologic conditions such as endometriosis), procedure characteristics, medications, and comorbid conditions (e.g., diabetes)—will be collected from all time in the database before the index date (which will be defined as the day of IUD insertion).

Patients will be followed from the time of IUD insertion until the first occurrence of any of the following: uterine perforation, IUD expulsion, IUD removal, indication of IUD reinsertion, indication of new pregnancy, hysterectomy, death, expiration of IUD (e.g., 5 years for Mirena), disenrollment from the database, or end of the study period. All person-time at risk that meets these criteria will be included, and there will be no requirement for minimum or maximum follow-up time. All IUD insertions occurring with at least 12 months of enrollment before the insertion that are noted within the data sources will be included in the study. The index date will be captured for each insertion, and baseline data will be collected for each index date. The main analyses for the study will assess only the first observed IUD insertion for each woman in the database. Secondary analyses will be conducted assessing all subsequent IUD insertions (i.e., after the first observed IUD insertion), as recorded in the database. The sequential number of each insertion as captured in the data for each woman will be collected and included as a baseline covariate within these secondary analyses.

9.2 Setting

This study will be conducted using data from four health care systems with EHRs: KPNC, KPSC, KPWA, and RI. The investigators at these sites (research partners) are working collaboratively to develop a common approach to study design and implementation as outlined in the following sections and detailed within the statistical analysis plan.

The exposure and outcome algorithms at all sites were developed collaboratively to capture the same concepts, but differ in specific terminology to the extent that there are differences across sites. Site investigators affiliated with each data system will be responsible for implementation of the

study protocol at their sites. Results will be summarized in a final study report by RTI Health Solutions (RTI-HS) in collaboration with the site investigators and Bayer AG.

9.2.1 Study time frame

Time windows

The earliest possible start for a patient to be eligible for the study population of women with IUD insertion will be 01 January 2001 (after approval of Mirena), and the latest date for a patient to be included in the study population will be 2 months before the end date of the data pull (anticipated to be about 30 June 2018* to coincide with anticipated approval of the protocol). The study start date at each site will be dictated by when EHRs were implemented or the time when Mirena was launched (RI). Further, the start date at each site for inclusion in the breastfeeding assessment will be dictated by the date at which breastfeeding data became available. The end date was chosen to coincide with the expected availability of complete data at the time of the data cut for the analysis. The start and end dates at each site are listed in Table 3.

Table 3. Start dates of EHR data and breastfeeding data and end date of study period, by data source

Site	Start date: EHR data	Start date: breastfeeding data	End date (date of data pull, based on anticipated approval of protocol)
KPWA	01 January 2006	01 January 2006	~30 June 2018
KPNC	01 January 2009	01 January 2009	~30 June 2018
KPSC	01 January 2008	01 January 2010	~30 June 2018
Regenstrief Institute	01 January 2001	01 January 2001	~30 June 2018

EHR = electronic health record; KPWA = Kaiser Permanente Washington; KPNC = Kaiser Permanente Northern California; KPSC = Kaiser Permanente Southern California.

Index date

The index date will be the date of IUD insertion.

9.2.2 Selection criteria

Inclusion criteria for the source population

Each IUD insertion is eligible for inclusion in the study if it meets *all* of the following criteria:

- Evidence in the database of insertion of an IUD (LNG-releasing, copper, or unidentified type) during the study time window for each site (through approximately 30 April 2018).
- Patient enrolled in the database with electronic medical records available for review for at least 12 months before the IUD insertion to ensure identification of any deliveries in the 12 months before IUD insertion and to provide a minimum time for capture of baseline data among IUD users.

* This study will be a retrospective analysis of secondary data. This end date for the data cut will be modified based on the timing of FDA approval of the study protocol in order to obtain the maximum data available at that time.

Exclusion criterion for the source population

IUD insertions will be excluded from the study if a patient meets the following criterion *at the time of the IUD insertion*:

- Aged more than 50 years at the time of the IUD insertion (IUD insertions that occur in eligible patients at younger ages will be included)

9.2.3 Study population

Source

This study will be conducted using EHR data from four health care systems: KPNC, KPSC, KPWA, and RI. The source population will be women with evidence, in their medical record, of insertion of an LNG-releasing IUD, a copper IUD, or an unidentified type of IUD during the study period and who were aged less than 50 years at the time of the IUD insertion. Only those with electronic medical records available for review beginning 12 months before the day of IUD insertion will be included in this study.

If women had more than one IUD insertion during the study period and were within the age limit at the time of the insertions, only the first observed IUD insertion will be included in the primary analyses. In a secondary analysis, each postinsertion period will be considered a separate at-risk period. Based on data from the validation study, this is anticipated to occur in 6% to 15% of the study population.

Sampling strategy

The first observed IUD insertion for each woman that meets study inclusion/exclusion criteria will be included in the primary analyses. All eligible IUD insertions occurring during the study period will be included in the study for secondary analysis.

Study population characteristics

The source population will include women in the US. Three of the data sources include individuals with health maintenance organization insurance coverage on the west coast of the US (Washington state, northern Idaho, and northern and southern California) and are ethnically diverse. The fourth data source is a health information exchange located in the midwest (Indiana), which includes all patients regardless of health insurance status and has a larger proportion of African Americans than the other sites but a lower proportion of other minorities.

9.3 Variables

9.3.1 Baseline characteristics

Baseline characteristics will be assessed before the index date for each eligible IUD insertion. The look-back time, all available data before the index date (unless otherwise specified for a particular variable), will be used to evaluate patient characteristics and the potential for confounding. Because all patients in the study are required to have at least 12 months of data before the first index date, there will be a minimum of 12 months of data from which to evaluate baseline characteristic values. For some patients, more information will be available, and all information within the database (see time frame for each database in Table 3) will be considered to reduce misclassification of baseline information (Brunelli et al., 2013).

Demographic characteristics

The following demographic variables will be assessed as potential confounders.

- **Age:** age in years as of the index date.
 - Three categories divided at tertiles (or closest integer cut point [i.e., in years]) for descriptive tables.
 - Continuous variable in propensity score models (including higher order terms age^2 and age^3 , if appropriate).
- **Race/ethnicity:** categorical variable with nine categories: non-Hispanic white, Hispanic white, non-Hispanic black, Hispanic black, other Hispanic, Asian/Pacific Islander, multiple races/ethnicities, other race/ethnicity, unknown
- **Smoking status:** indicator variable (0 = no recent smoking, 1 = recent smoking [active smoker within 365 days before index date]) for smoking status as of the index date, where available (i.e., KPSC; partial KPWA, RI).
- **Calendar year of the index date:** year of IUD insertion.
- **Month of the index date:** 12-level categorical variable corresponding to month of the IUD insertion.
- **Duration of the look-back period at the index date:** continuous variable with a minimum of 365 days may be categorized after examining frequency distribution.

Clinical characteristics

- **Body mass index (BMI):** continuous variable assessed at the index date or the closest date before or after the index date.
 - If BMI is not recorded within the EHR, then weight and height closest to the index date (before or after the index date) will be used to calculate BMI (weight [in kg] divided by height [in meters] squared, kg/m^2).
- **Dysmenorrhea:** four-level categorical variable for whether the patient was diagnosed with dysmenorrhea
 - Diagnosed in the year prior to the index date, but not diagnosed before that time
 - Not diagnosed in the year prior to the index date, but was diagnosed before that time
 - Diagnosis recorded both within year prior to the index date and before that time
 - No diagnosis of dysmenorrhea within data
- **Fibroids:** indicator variable (0 = No, 1 = Yes) for whether the patient was ever diagnosed with or reported diagnosis of uterine fibroids prior to the index date.
- **Parity:** cumulative number of viable pregnancies (i.e., carried to at least 20 weeks gestation) prior to the index date..

The following baseline characteristics will be captured only among women who had at least one delivery prior to the index date:

- **Cesarean delivery** will be captured in two variables:
 - Indicator variable (0 = No, 1 = Yes) for whether the patient ever had a Cesarean delivery prior to the index date.
 - Indicator variable (0 = No, 1 = Yes) for whether the patient had a Cesarean delivery for the most recent delivery that is within 52 weeks prior to the index date.

Procedure-related characteristics

- **Concomitant gynecological procedure:** indicator variable (0 = No, 1 = Yes) for whether the IUD insertion was performed during the same visit as another gynecological procedure or surgery.
 - The following will be considered concomitant gynecological procedures: abortion, aspiration and curettage, dilation and curettage, excision/biopsy of cervix or uterus, ablation, colposcopy, hysteroscopy, laminaria, laparoscopy, lysis adhesions, myomectomy, nerve procedure, salpingectomy/oophorectomy. If insufficient data are available to assess (RI only), then concomitant gynecological procedures will be missing.
- **IUD insertion count:** count of the number of IUD insertions for this woman, including the current insertion, that was identified before or on the index date within the data source.
- **Initial IUD insertion:** indicator variable (0 = No, 1 = Yes) for first insertion seen within data.

Indicators of a difficult IUD insertion

- **Difficult insertion:** indicator variable (0 = No, 1 = Yes) for whether any of the following occurred on the index date (or in the 7 days before the index date for misoprostol): *cervical dilation, ultrasound guidance, paracervical block, provider note, use of misoprostol*
- **Cervical dilation** will be identified on the day of the IUD insertion and will be classified as yes or no. If there is no information in the record that cervical dilation was done, then the classification will be “no.”
- **Ultrasound guidance** for the placement of the IUD will be identified on the day of the IUD insertion and will be classified as yes or no. If there is no information in the record that ultrasound guidance was used, then the classification will be “no.”
- **Paracervical block:** indicator variable (0 = No, 1 = Yes) for whether the patient received a paracervical block during the IUD insertion procedure. If there is no information in the record that a paracervical block was used, then the classification will be “no.”
- **Provider note indicating a difficult insertion or complicated procedure:** indicator variable (0 = No, 1 = Yes) for whether the patient record includes a notation from the provider regarding a difficult insertion or complicated procedure. If there is no notation of this in the record, then the classification will be “no.”
- **Use of misoprostol:** indicator variable (0 = No, 1 = Yes) for whether the patient received misoprostol during the 7 days before the IUD insertion procedure.

Provider-related characteristics, where available (i.e., KPNC, KPSC, KPWA)

- **Provider number of IUD insertions in the previous year:** number of IUD insertions the provider performed in the previous year.
- **Provider annualized number of IUD insertions in the previous year:** provider number of IUD insertions in previous year divided by the number of months provider was employed by health care system represented in data source.
- **Categorical indicator for number of IUD insertions in the previous year:** 0 = fewer than 50 IUD insertions in the previous year, 1 = 50 or more IUD insertions in the previous year.
- **Provider length of employment in the previous year:** continuous variable of the number of days employed within the health care system in the past year.

9.3.2 Exposure

- **Pregnancy delivery date** is the date on which delivery occurred.
- The **days postpartum** will be calculated as the difference between the date of the most recent delivery and the IUD insertion date and will be expressed in days. Data for days postpartum will not be captured for women with no evidence of delivery in the past year (52 weeks).
- **Postpartum status** will consist of three variables: two dichotomous variables and a four-level categorical variable. In all of these variables, women with no evidence of delivery in the past year (52 weeks) will be classified as “no delivery in the past 52 weeks.”
 - **Postpartum status categories for primary objective** will consist of the following four categories (as proposed by the FDA).
 - ≤ 6 weeks postpartum
 - > 6 weeks and ≤ 14 weeks postpartum
 - > 14 weeks and ≤ 52 weeks postpartum
 - > 52 weeks postpartum (including women without recorded delivery in the past 52 weeks)
 - **Postpartum status at IUD insertion for sensitivity analysis** will be a dichotomous comparison of ≤ 14 weeks postpartum versus > 14 weeks postpartum (including women with no evidence of delivery in the past year [52 weeks]).
 - **Postpartum status similar to EURAS-IUD** will be a dichotomous comparison of IUD insertions occurring ≤ 36 weeks postpartum versus > 36 weeks postpartum (including women with no evidence of delivery in the past year [52 weeks]).
- **Breastfeeding status** at the time of IUD insertion: any evidence of breastfeeding (i.e., any breastfeeding or pumping across a 24-hour period) at the time of IUD insertion will be determined based on linked mother/infant records (e.g., well-child visits, infant check-ups, and immunization visits) and clinical notes for the woman and infant. Breastfeeding status will be classified as yes (last breastfeeding date within 14 days before IUD insertion or after IUD insertion), no (last breastfeeding date more than 14 days before IUD insertion; first non-breastfeeding date before IUD insertion), or undetermined. Breastfeeding status will not be ascertained for women with no evidence of a live birth in the past year (52 weeks) and those women will be classified as not breastfeeding.

- **IUD type:** three-level categorical variable of inserted IUD type:
 - LNG-IUD: Mirena, Liletta, Skyla, Kyleena
 - Copper IUD: ParaGard, other copper
 - Unknown IUD type
- **Menorrhagia: diagnosis of menorrhagia will be assessed in two variables**
 - As an exposure: indicator variable (0 = No, 1 = Yes) for whether the patient was diagnosed with menorrhagia in the year (365 days) prior to the index date
 - As a covariate within other exposure assessments: four-level categorical variable for whether the patient was diagnosed with menorrhagia
 - Diagnosed in the year prior to the index date, but not diagnosed before that time
 - Not diagnosed in the year prior to the index date, but was diagnosed before that time
 - Diagnosis recorded both within the year prior to the index date and before that time
 - No diagnosis of menorrhagia within data

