9.7.2.1 Study cohorts defined by exposure variables

Only women with eligible IUD insertions and nonmissing exposures will be included in analyses reliant on exposure status. Three cohorts of interest are defined based on need for nonmissing data:

- **Complete study population:** all first IUD insertions included in the data* based on study inclusion and exclusion criteria outlined in Section 9.2.2. This study cohort will include women with missing data for breastfeeding status, and/or IUD type.† The missing data within breastfeeding status and IUD type may be considered a separate group within the analyses.
- **Breastfeeding status:** all IUD insertions among women who were less than 52 weeks postpartum at the time of IUD insertion and had either “yes” or “no” breastfeeding status at the

* Objectives 18 and 23 are the only objectives that assess all IUD insertions. All other objectives assess only the first IUD insertion within the data for each woman.

† No missing data are anticipated for postpartum/no delivery status or menorrhagia. For both of these variables, lack of documentation associated with the variable would default the status for that IUD insertion to the unexposed or referent category of the variable.

time of IUD insertion will be included in this cohort. IUD insertions among women who have undetermined breastfeeding status will not be included.

- **IUD type:** all IUD insertions with a known type of IUD (either LNG-IUD or copper IUD) will be included in this cohort. IUD insertions among women who had an undetermined IUD type will not be included.

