There is potential for underreporting of outcomes within the data sources since women will need to seek treatment in order to have an outcome diagnosed. Asymptomatic perforation or IUD expulsion may not be captured. In addition, there may be a lag time between occurrence of perforation or IUD expulsion and the time that the woman seeks treatment. So there is the possibility of missing outcome occurrence. However, this approach is representative of the way that these outcomes would appear within clinical practice, is similar to EURAS-IUD, and there is no reason to believe that this would be differential by exposure group (e.g., breastfeeding vs. not breastfeeding at the time of IUD insertion). So the absolute incidence rates may not be entirely accurate because of potential underestimation due to underreporting or inaccurate coding; or potential overestimation if the algorithm identifies outcomes (e.g., uterine perforation) that are not true cases. However, the ratios should provide an unbiased estimate of any differential risk between exposure groups. We will also assess rates of uterine perforation and IUD expulsion in the literature to provide an external context for the incidence rates.

There is potential for misclassification and missingness of breastfeeding status at the time of IUD insertion. Data sources obtain information for this variable in different ways, with some utilizing linkage to well-child visits for the infant and others using data from the woman's chart either for postpartum visits or on the date of IUD insertion. The complexity of identifying the information within the charts is somewhat mitigated through the involvement of both clinicians and seasoned data informaticists working within each health care system who have experience with identifying such information. Further, the classification of breastfeeding as yes or no is a crude dichotomy and does not follow the potential biological mechanism for breastfeeding to affect uterine perforation or IUD expulsion. For example, breastfeeding once per day differs from eight times per day (the recommendation from one research partner), and thus combining all breastfeeding into one category combines a heterogeneous experience.

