Patients will be followed from the time of IUD insertion until the first occurrence of any of the following: uterine perforation, IUD expulsion, IUD removal, indication of IUD reinsertion, indication of new pregnancy, hysterectomy, death, expiration of IUD, disenrollment from the database, or end of the study period. All person-time at risk that meets these criteria will be included, and there will be no requirement for minimum or maximum follow-up time. All IUD insertions occurring with at least 12 months of enrollment before the insertion that are noted within the data sources will be included in the study. The index date will be captured for each insertion, and baseline data will be collected for each index date (Figure 2). The main analyses for the study will

assess only the first observed IUD insertion for each woman in the database. Secondary analyses will be conducted assessing subsequent insertions (i.e., not the first IUD insertion), as recorded in the database. The sequential number of each insertion, as captured in the data for each woman, will be collected and included as a baseline covariate within these secondary analyses.

Figure 2. Covariate data collection around index date

Exposures of postpartum status (based on pregnancy delivery date), breastfeeding status, IUD type, and menorrhagia (as a proxy for indication of use) will be assessed as of the index date of IUD insertion. Outcomes of uterine perforation and IUD expulsion will be assessed beginning on the index date. Baseline data—such as patient demographics, patient characteristics (e.g., personal history of gynecologic conditions such as endometriosis), procedure characteristics, medications, and comorbid conditions (e.g., diabetes)—will be collected from all time in the database before the index date (which will be defined as the day of IUD insertion) and on the index date (Figure 2). Provider characteristics, procedure-related characteristics, and indicators of a difficult insertion will be assessed on the index date (i.e., on the same date or within the same encounter as the index date). The variables to be obtained from each research site are provided in Sections 3.1 through 3.8.

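### Breastfeeding status can be set by records made after insertion, including outcome work-ups, so exposure in objectives 1 and 20 can depend on the outcome, and no planned analysis tests this

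*Protocol*

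**What the plan says.** Protocol 9.3.2 defines *Yes* as "yes (last breastfeeding date within 14 days before IUD insertion or after IUD insertion". It sets no upper limit on how long after insertion. The other labels are "no (last breastfeeding date more than 14 days before IUD insertion; first non-breastfeeding date before IUD insertion), or undetermined". Both *No* conditions are dates before insertion, and the semicolon does not say whether they join as AND or OR.

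The sources are linked mother and infant records, such as well-child visits, "infant check-ups, and immunization visits) and clinical notes for the woman and infant". Nothing there sets a cut at the outcome date or excludes notes from an outcome visit. Protocol 9.9 adds that sites differ: some use infant visits, "others using data from the woman's chart either for postpartum visits or on the date of IUD insertion".

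Undetermined women leave the analysis. Protocol 9.7.2.1 states that "IUD insertions among women who have undetermined breastfeeding status will not be included", and SAP 5.1.2 says the same of Analysis Set 2, the set for objectives 1 and 20.

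Three other places bear on timing. Protocol 9.1 uses the 12 months of enrolment before insertion to gather breastfeeding data. SAP Section 3 says the exposures "will be assessed as of the index date of IUD insertion". SAP 3.1 lists the three labels with no window. None of these is reconciled with Protocol 9.3.2.

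**The concern.** A post-insertion note that documents breastfeeding moves the last breastfeeding date past insertion and so makes the woman *Yes*. She may come from *Undetermined* or, if the *No* conditions join as OR, from *No*. A later entry that she is not breastfeeding, without a stop date before insertion, cannot make her *No*.

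A woman with a perforation or expulsion has extra encounters in which lactation may be noted. If those notes count, the outcome helps decide who enters the exposed group. That is outcome-dependent exposure ascertainment in a primary comparison with about 78 expected events, where a few cases matter. Overlap weighting balances covariates; it does not correct how the exposure was ascertained.

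Nothing planned would reveal it. The one sensitivity analysis for objective 1 (SAP 6.2.1) changes only the method of covariate adjustment, and the expulsion objectives have none (SAP 6.3.1). Protocol 9.9 acknowledges misclassification and missingness of breastfeeding status, but not dependence on the outcome. Its remark that errors should not differ by exposure group concerns under-reporting of outcomes.

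**Working it through.** **Inputs (Protocol 9.5 and Table 4).** 225,000 first insertions; 60,000 with breastfeeding status; about 30% inserted within 52 weeks postpartum; 60:40 breastfeeding to not; 1.3 perforations per 1,000 insertions; two-sided alpha 0.05.

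**Reproducing the plan's figure.** Events = 60,000 × 0.0013 = 78. Schoenfeld power = Φ(√(78 × 0.6 × 0.4) × ln HR − 1.96). For HR 1.5, 1.75, 2.0, 2.25 and 2.5 this gives 41.9, 67.8, 85.1, 93.9 and 97.8%, against 42, 68, 85, 94 and 98% in Table 4. No stated figure is in dispute.

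**Expected cases at a true HR of 1.**
- *Yes*: 36,000 × 0.0013 = 46.8. *No*: 24,000 × 0.0013 = 31.2.
- Undetermined women: 0.30 × 225,000 − 60,000 = 7,500, with 7,500 × 0.0013 = 9.75 cases.
- Assuming 60% of them breastfeed at the same risk: 5.85 breastfeeding cases.

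**Only cases gain records; *Undetermined* to *Yes*.** With a share q of the 5.85 moved, HR = [(46.8 + 5.85q)/36,000] / [31.2/24,000]. Type I error uses a normal approximation with SE = √(1/*Yes* cases + 1/*No* cases).

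| q | Cases added | HR read at true 1.0 | Type I error |
|---|---|---|---|
| 0.10 | 0.58 | 1.01 | 5.0% |
| 0.25 | 1.46 | 1.03 | 5.2% |
| 0.50 | 2.92 | 1.06 | 5.8% |
| 1.00 | 5.85 | 1.125 | 8.2% |

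A true HR of 2.0 would read 2.125 at q = 0.5 and 2.25 at q = 1.

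With 60% breastfeeding in both pools, the ceiling is 1 + undetermined/60,000. The 7,500 is a difference of rounded figures: 29% or 31% in place of 30% gives 5,250 or 9,750, and a ceiling of 1.09 or 1.16.

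**Non-cases gain records too.** Of 4,500 breastfeeding undetermined women (0.6 × 7,500), a share s joins the *Yes* denominator.
- Cases 50%, non-cases 50%: (46.8 + 2.925)/(36,000 + 2,250) = 0.0013, so HR 1.00.
- Cases 50%, non-cases 25%: HR 1.03.
- Cases 25%, non-cases 50%: (46.8 + 1.46)/38,250 = 0.00126, so HR 0.97.

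**OR reading; *No* to *Yes*.** If a fraction f of the *No* group is in fact breastfeeding and a share q of those cases (no non-cases) is moved, HR = [(46.8 + 31.2fq)/36,000] / [31.2(1 − fq)/24,000]. For f = 5, 10 and 20%, this gives 1.04, 1.09 and 1.19 at q = 0.5, and 1.09, 1.19 and 1.42 at q = 1.

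Every q, s and f is an assumption; the documents give none.

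**The case against.** The strongest reply has four parts.

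1. *The asymmetry has a logical basis.* A later breastfeeding record for the same infant is normally good evidence of breastfeeding at insertion. A later not-breastfeeding entry says little about the insertion date. This stands: under AND the problem is mainly selective entry from *Undetermined*, not false *Yes* labels.

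2. *Non-cases have later records too.* Well-child and immunization visits continue for everyone, and late perforations are unlikely to coincide with breastfeeding of that infant. This also stands. A reader might infer that the rule itself pushes the hazard ratio up. The documents do not support that, because direction depends on relative capture, which they do not report. Unequal capture is nevertheless plausible where status comes from the woman's chart. It is plausible too at KPWA, whose mother-infant database ran only through 2015 (Protocol 9.4.3) while insertions run to about April 2018 (9.2.2).

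3. *The dates are of breastfeeding, not of records.* A reader might infer that no later record can ever yield *No*. That is too strong: a later note giving a stop date before insertion can.

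4. *AND is the more natural reading.* Under OR, a last breastfeeding date 10 days before insertion and a first non-breastfeeding date 3 days before would satisfy both labels. Consider a woman last recorded as breastfeeding 20 days before insertion, with no non-breastfeeding record. She is *No* only under OR; under AND she is *Undetermined*. Under AND, a *No* could become *Yes* only if a later note contradicted a recorded pre-insertion stop. The larger shifts therefore cannot be presented as the expected effect.

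SAP Section 4 also places operational definitions in a separate template, so site practice may be stricter than the text. The general statements in Protocol 9.1 and SAP Section 3 do not, however, override the explicit rule in 9.3.2.

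**Conclusion.** The point holds as a defect in the stated exposure rule, not as a demonstrated upward bias. As written, records generated by the outcome can decide whether a woman enters the exposed group in objectives 1 and 20, and no planned analysis would show it.

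For objective 1, if only cases gain records and half to all of the roughly 6 breastfeeding undetermined cases move, a true HR of 1.0 reads about 1.06 to 1.125, with type I error about 6% to 8%. This rests on about 7,500 undetermined women, 60% of them breastfeeding, at the common perforation risk. Equal capture gives no bias; greater capture in non-cases gives a downward shift (0.97 in the example). Larger upward shifts belong to the OR reading with assumed flip rates and should not be quoted as findings. No expulsion rate is given, so type I error for objective 20 was not calculated.

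**What to change.** 1. In Protocol 9.3.2 and SAP 3.1, do not use maternal records dated on or after the first suspicion or confirmation of perforation or expulsion to set breastfeeding status. Apply the same post-insertion record window to *Yes* and *No*. The window matters: a cut at the outcome date alone leaves non-cases with longer maternal follow-up. If non-cases were captured at 50% and cases at none, a true HR of 1.0 would read (46.8/38,250)/0.0013 = 0.94.
2. Join the two *No* conditions as AND. A woman whose last record is of breastfeeding more than 14 days before insertion, with no non-breastfeeding record before insertion, is then *Undetermined*. Align Protocol 9.1, Protocol 9.3.2 and SAP 3.1.
3. Add a sensitivity analysis of objectives 1 and 20 using only records dated on or before the index date. A small table of record source and date by case status would show whether capture in fact differs.

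The cost is a change to the site extraction rule and a few tables. Some women move to *Undetermined*, so the 60,000 and the power in Table 4 fall by an amount the documents do not allow to be quantified.
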